1.2 Overview

This study will evaluate STEP-YA in an RCT of 74 off-treatment YACS (ages 20-39). As individualized coaching is an effective component of behavioral interventions for cancer survivors and other populations,⁴²⁻⁴⁴ we are interested in evaluating their utility for supporting STEP-YA outcomes. Study participants will be assigned (1:1) to receive the STEP-YA intervention either, 1) alone (non-coaching condition), or 2) with the addition of 2 remote coaching sessions (coaching condition). STEP-YA sessions will be delivered online using the Zoom platform, which is currently in use at DFCI for virtual patient visits and education programs. Participants will complete measures of insomnia and mood at baseline and again at 4- and 8-weeks post-baseline. A repeated-measures design, with each subject acting as their own control, enables the trial to efficiently evaluate potential efficacy of STEP-YA (phase IIa “proof of concept” objective). Randomization to a coaching condition makes it possible to evaluate utility of remote coaching to improve STEP-YA outcomes (phase Ib objective). As coaching sessions add significantly to costs and complexity, a goal of this study is to determine if they have potential to augment STEP-YA effects before including them in any future Phase III efficacy trials of STEP-YA.

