5.3 STEP-YA Intervention

STEP-YA is delivered in a single 90-minute synchronous videoconference session using HIPAA compliant Zoom technology⁴⁶⁻⁴⁸ licensed to our cancer center. Interventionists with graduate level training in psychology, social work, or closely aligned discipline (e.g., human development,

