
5.4 Behavioral Coaching

Participants randomized to the coaching condition will receive 2 individualized remote coaching sessions 1, and again 2 weeks following their STEP-YA session. Optimal timing for coaching sessions is 7 and 14 days after the STEP-YA session, but may be scheduled between 5-23 days after the STEP-YA session with at least 5 days between coaching sessions. Paraprofessional coaches trained and supervised by psychologists with CBTI expertise will follow a structured outline adapted from a previous self-management intervention at our center.⁵⁴ In the sessions, designed to last approximately 30 minutes, coaches ask participants to review their progress and challenges implementing their sleep action plan. Coaches offer support and encouragement and may refer participants to the take-home materials to help answer questions and reinforce program goals and suggestions. Following, principles of self-care management and previous coaching interventions successful with cancer survivors,^{44, 55-58} coaching sessions are not prescriptive, but support YACS to use self-management skills including decision-making, goal-setting, self-assessment, and problem solving to help them implement their individual sleep action plan. Administrative data on coaching session duration, and sessions missed, interrupted, or rescheduled will be collected.

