7.0 STATISTICAL ANALYSIS

Primary Aims:

1. To test the hypothesis that STEP-YA improves insomnia symptoms (primary outcome) and mood (secondary outcome) in young adult cancer survivors.

2. To determine if improvement in these outcomes are superior in the coaching condition compared to the non-coaching condition. This is a randomized 2-arm trial evaluating the STEP-YA intervention when delivered with and without supplementary remote coaching session. Immediately after completing baseline assessment subjects will be randomized (1:1 by the Sealed Envelope system) to receive the STEP-YA intervention either, 1) alone (**Non-Coaching condition**), or 2) with the addition of 2 remote coaching sessions delivered in the two weeks following the intervention session. (**Coaching condition**). Randomization, with block size of 4, will be stratified by age category (20-29 years vs. 30-39 years). Primary endpoint is change in Insomnia Severity Index score from baseline to 8-weeks post-intervention. Secondary endpoint is change in mood symptoms on the Profile of Mood States-Short Form from baseline to 8-weeks post-intervention. Primary and secondary endpoints are change at 8 weeks; data collected at 4-week post-assessment will be analyzed using similar methods for descriptive and exploratory purposes.

Data analysis for this study will follow methods used for our recently completed clinical trial of in-person insomnia interventions delivered to cancer survivors (1R03CA201459). Change scores will be treated as continuous variables and primary analyses will compare the arms using 2-way analysis of variance with one between-subjects factor (Coaching vs. Non-Coaching) and one within-subjects factor (time). Cohen's d will be used to quantify within-group effect sizes and Hedges' g adjustment will estimate between-group effect sizes. Aim 1 will be addressed using a

within-subjects analysis including all participants to determine if the STEP-YA intervention is associated with significant changes in outcome measures over time. Aim 2 will be addressed with an analysis that includes both the within – and between-subjects factors as well as an interaction term to determine if the effect of the intervention differs between Coaching and non-Coaching groups (i.e. significant interaction term).

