Sample Size/Power: To meet our aims we require 64 participants with evaluable data but will enroll 74 as a hedge against attrition. Our prior single-session educational interventions have demonstrated large effects of $d \geq 1.00$; the study is conservatively powered to detect an effect size of .52 (Primary Aim). With sample size of 64 (32 per arm), the study will have 80% power to detect an effect of this size within each arm ($\alpha=0.05$). To compare the relative improvement in the primary endpoint between arms, $N=64$ subjects will have 80% power to detect a difference of $d=0.62$ between arms ($\alpha=0.05$, one-sided).

Secondary Aim: *Explore participant variables associated with clinically significant response to the STEP-YA intervention.* Logistic regression will be used to identify demographic and sleep factors (e.g., age, severity of insomnia symptoms) associated with a reduction of ISI scores ≥ 6 points at 8 weeks. Variables identified in univariate analysis ($p<.10$) will be entered into a multivariable model estimating STEP-YA response from baseline variables. Analyses will explore these relationships separately in the two study arms; Pooled analyses including participants across arms will be conducted if univariate analyses indicate relationship of predictors and outcome are consistent.

Missing Data: Participants will be randomized after completing a baseline so complete baseline data are assured. Primary analysis will be an intent-to-treat analysis of randomized subjects. Based on experience using similar data collection methods, we anticipate minimal missing data ($<10\%$). If needed, we will use multiple imputation to account for missing data. Potential factors in the imputation model include baseline sleep and mood variables. Sensitivity analysis will be used to evaluate the potential impact of imputation on results.

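### Several coaches work in one arm only, but the Aim 2 analysis and its power treat participants as independent; if coaches differ, the standard error of the coaching effect is too small for a conclusion about coaching in general

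*Combined protocol and SAP*

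**What the plan says.** Section 7.0 (Statistical Analysis) states that "primary analyses will compare the arms using 2-way analysis of variance with one between-subjects factor (Coaching vs. Non-Coaching", with time as the within-subjects factor. Aim 2 is tested by the arm-by-time interaction. The same section claims "80% power to detect a difference of $d=0.62$ between arms ($\alpha=0.05$, one-sided", based on 64 evaluable participants: "With sample size of 64 (32 per arm". It contains no coach term, cluster-robust error, design effect or sensitivity analysis for clustering. The only sensitivity analysis it names concerns imputation.

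Section 5.4 (Behavioral Coaching) describes who delivers the two sessions: "Paraprofessional coaches trained and supervised by psychologists with CBTI expertise will follow a structured outline". The plural shows that there is more than one coach. Their number, their caseloads and how participants are assigned to them are not stated, nor is it stated whether one coach gives both sessions. The coaching data listed there cover session length and disrupted or missed sessions; coach identity is not listed.

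Section 1.2 (Overview) gives the purpose of the coaching comparison: to "determine if they have potential to augment STEP-YA effects before including them in any future Phase III efficacy trials of STEP-YA".

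**The concern.** The design is partially nested. Participants in the coaching arm share coaches, while each participant in the other arm stands alone. If one coach gets better results than another, the outcomes of that coach's participants are correlated, and the mean of the coaching arm varies more than independent observations would. An ANOVA with arm as its only between-subjects factor leaves that extra variation out of the standard error.

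Whether this matters depends on the question. A statement about these particular coaches does not need coach as a source of error. The decision in section 1.2 is whether coaching as a component belongs in a later trial, and that trial may use other people. For that question, the choice of coaches is part of the sampling error. With few coaches, a good or poor one can be read as an effect of coaching. The interval carried into planning would then be too narrow and the power statement too favourable. If coach identity is not recorded, none of this can be examined afterwards.

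**Working it through.** **Inputs from the documents.** 32 evaluable participants per arm, d = 0.62, α = 0.05 one-sided, power 80% (section 7.0); coaching in one arm only, coaches in the plural (section 5.4).

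**Assumptions, because the documents give no figure.** k = 2 to 6 coaches with equal or near-equal caseloads; coach ICC of the ISI change score from 0.02 to 0.10; total variance equal in both arms.

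**Step 1: reproduce the plan's figure.** For change from baseline to 8 weeks, the arm-by-time interaction is a two-sample comparison of change scores. The noncentrality is 0.62 × √(32/2) = 0.62 × 4 = 2.48. Normal approximation: power = Φ(2.48 − 1.645) = 79.8%. Noncentral t on 62 degrees of freedom: 79.0%. The stated 80% therefore reproduces, one-sided and with independent participants. A two-sided test gives 68.5% to 69.8%.

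**Step 2: effect of coach clustering.** With m = 32/k participants per coach:

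- design effect in the coaching arm: DE = 1 + (m − 1) × ICC
- true SE divided by modelled SE: r = √((DE + 1)/2), since only one of the two arms is affected
- approximate one-sided type I error of the planned test: 1 − Φ(1.645/r)
- one-sided power at d = 0.62 with the correct SE: Φ(2.48/r − 1.645)

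Example, 3 coaches and ICC 0.05: m = 10.67; DE = 1 + 9.67 × 0.05 = 1.48; r = √(2.48/2) = 1.114; type I error = 1 − Φ(1.477) = 7.0%; power = Φ(2.226 − 1.645) = 72% (71% with the t distribution).

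**Step 3: the range.** The type I columns come from simulating the unadjusted t-test (100,000 trials per cell). The one-sided results agree with the formula to within 0.5 points.

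| Coaches | ICC | DE | r | Type I, one-sided | Type I, two-sided | Power with correct SE (one-sided) |
|---|---|---|---|---|---|---|
| any | 0 | 1.00 | 1.00 | 5.0% | 5.0% | 80% |
| 6 | 0.02 | 1.09 | 1.02 | 5.3% | 5.4% | 78% |
| 4 | 0.02 | 1.14 | 1.03 | 5.5% | 5.7% | 77% |
| 4 | 0.05 | 1.35 | 1.08 | 6.5% | 7.0% | 74% |
| 3 | 0.05 | 1.48 | 1.11 | 7.0% | 7.9% | 72% |
| 2 | 0.05 | 1.75 | 1.17 | 8.2% | 9.6% | 68% |
| 2 | 0.10 | 2.50 | 1.32 | 11.2% | 14.4% | 59% |

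The power column is a normal approximation and does not yet count the degrees of freedom lost when the coach variance has to be estimated. The two-sided column is shown because the one-sided α appears only in the power statement; section 7.0 gives no sidedness for the interaction test itself.

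**Step 4: what a nested test would cost.** I simulated a test that uses the between-coach mean square in the coaching arm, with Satterthwaite degrees of freedom (100,000 trials per cell, 32 per arm, d = 0.62, one-sided). With no coach effect at all, power falls from 79% to about 65% with 2 coaches and about 71% with 3. At ICC 0.05 it is about 52% and 61%. With 2 coaches the test still rejects a true null about 6% to 7% of the time.

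**The case against.** The strongest objection is that the inflation is conditional. A reader might infer that the false-positive rate of the Aim 2 test does exceed 5%. The documents do not support that. It requires a non-zero coach ICC, which they do not give, and its size depends on a number of coaches that they do not give either. If coaching does nothing with any coach, coaching creates no coach variance and the test holds its level. The excess arises only under a null of zero average effect over coaches who do differ. This stands, and the verdict is worded accordingly.

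Second, the plan limits variation between coaches: training, supervision, a structured outline, and two sessions of about 30 minutes. At ICC 0.02 with 4 to 6 coaches the excess is about half a percentage point. This stands as a reason to expect a small ICC, but not a zero one, because section 5.4 also describes the sessions as individualized and non-prescriptive.

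Third, section 1.2 presents the coaching comparison as an early-phase objective, so a modest excess may be tolerable. That argues against replacing the primary model, and Step 4 supports it. It does not argue against recording who coached whom.

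A reader might also extend the point to the STEP-YA session, since section 5.3 uses the plural there as well: "Interventionists with graduate level training in psychology, social work, or closely aligned discipline". Section 5.2 shows why this fails. The session comes before randomization and the interventionist is blind to the arm, so any clustering by interventionist is not confined to one arm.

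**Conclusion.** The point holds in conditional form. The documents confirm that several coaches work in one arm only, that arm is the only between-subjects factor in the Aim 2 model, that neither the model nor the power allows for coach clustering, and that coach identity is not among the listed coaching data. If coaches differ, the planned standard error is too small for a conclusion about coaching in general.

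Under the assumed range of 2 to 6 coaches and ICC 0.02 to 0.10, the true standard error is 1.02 to 1.32 times the modelled one, and the one-sided type I error is about 5.3% to 11%. The upper end needs both the fewest coaches and the largest ICC. The 80% power is correct as arithmetic but holds only with no coach effect. Aim 2 is one of the two primary aims and informs the Phase III decision, so a cheap safeguard is worth adding; a change of primary analysis is not.

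**What to change.** - **Conduct.** State the number of coaches and how participants are assigned to them. Record coach ID for each coaching participant, keep one coach for both sessions where possible, and spread participants evenly over coaches.
- **Primary analysis.** Keep the planned ANOVA for Aim 2.
- **Sensitivity analysis, pre-specified in section 7.0.** Fit a partially nested model with a coach random effect in the coaching arm only and small-sample degrees of freedom (Satterthwaite or Kenward-Roger). With only two or three coaches, instead report mean change by coach and repeat the arm test with the SE inflated for ICC 0.02, 0.05 and 0.10 (multiply by r from Step 2, using the actual caseloads).
- **Interpretation.** If the conclusion changes, limit it to these coaches.
- **Power.** State that the 80% at d = 0.62 assumes no coach effect.

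The cost is one data field, a few lines of text and a little more analysis, with no extra participants or visits. With few coaches the nested analysis is imprecise and has clearly lower power, so it should qualify the primary test and not replace it.

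### The Aim 2 power figure is for a one-sided test, but Aim 2 is to be decided by a non-directional interaction test with no stated alpha or direction

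*Combined protocol and SAP*

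**What the plan says.** All the relevant text is in section 7.0 of the combined protocol and SAP.

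- **Aim 2** is worded directionally: "To determine if improvement in these outcomes are superior in the coaching condition compared to the non-coaching condition".
- **Model.** The primary analyses use a "2-way analysis of variance with one between-subjects factor (Coaching vs. Non-Coaching) and one within-subjects factor (time"). For Aim 2 an interaction term is added, "to determine if the effect of the intervention differs between Coaching and non-Coaching groups (i.e. significant interaction term"). No alpha level and no direction are given for this test.
- **Endpoint.** The primary endpoint is change in the Insomnia Severity Index from baseline to 8 weeks. The 4-week data are descriptive and exploratory.
- **Power (Sample Size/Power paragraph).** For the between-arm comparison, 64 participants are said to give "80% power to detect a difference of $d=0.62$ between arms", at "\alpha=0.05$, one-sided". The sentence before it gives 80% power within each arm at an effect of 0.52 and alpha 0.05, with no side named.
- **Numbers.** "With sample size of 64 (32 per arm"); "we require 64 participants with evaluable data but will enroll 74 as a hedge against attrition".

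**The concern.** A power figure should describe the test that will decide the aim. Here the sample-size paragraph describes a one-sided test, while the analysis text describes an ANOVA interaction, which rejects for a difference in either direction. An analyst who follows the analysis text and uses the customary 0.05 level runs a less powerful test than the one for which power is stated.

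Two things are at stake. The chance of missing the effect for which the comparison was sized may be larger than the 20% that the plan implies. The criterion for success is also ambiguous: an interaction that favours coaching with an F-test p-value between 0.05 and 0.10 would count as positive under the power paragraph and as negative under the analysis text at 0.05. That choice should not be left open until the result is known.

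**Working it through.** **Inputs (section 7.0).** n = 32 evaluable per arm (64 in total, 1:1), d = 0.62 on the change-score SD, alpha = 0.05. The endpoint is 8-week change, so the time factor has two levels (baseline, 8 weeks).

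**Step 1: link the two tests.** With two time levels, the arm-by-time interaction has 1 degree of freedom. Its F(1,62) is the square of the two-sample t on change scores (df = 2×32 − 2 = 62). The F test at 0.05 is therefore the two-sided t test at 0.05.

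**Step 2: reproduce the plan's figure.** The noncentrality is d×√(n/2) = 0.62×√16 = 2.48. The one-sided 0.05 critical value is t(0.95; 62) = 1.670. Power = P(T > 1.670), with T noncentral t (df 62, noncentrality 2.48), which is **79.0%**. The normal approximation gives 79.8%. The stated 80% is reproduced.

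**Step 3: power of the F test at 0.05.** The noncentrality is 2.48² = 6.15 and the critical value is F(0.95; 1, 62) = 3.996 (|t| > 1.999). Power is **68.5%** (normal approximation 69.8%), so the chance of missing d=0.62 is 31.5%.

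**Step 4: detectable effect and sample size.**

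| Evaluable per arm | One-sided 0.05, power at d=0.62 | F test at 0.05, power at d=0.62 | d for 80% power, one-sided | d for 80% power, F test |
|---|---|---|---|---|
| 32 | 79.0% | 68.5% | 0.63 | 0.71 |
| 37 (all 74) | 84.1% | 74.9% | 0.58 | 0.66 |

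For 80% power at d=0.62, the F test at 0.05 would need 42 evaluable per arm (84 in total).

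**Step 5: the zone where the two readings disagree.** With 32 per arm the standard error of the standardised difference is about √(2/32) = 0.25. The one-sided test succeeds when the observed difference exceeds 1.670×0.25 = 0.42. The F test needs 1.999×0.25 = 0.50. An observed difference of about 0.42 to 0.50 SD in favour of coaching passes one test and fails the other. This is the same zone as F-test p between 0.05 and 0.10.

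**Step 6: the within-arm figure in the same paragraph.** For a paired t test with n = 32 and d = 0.52, the noncentrality is 0.52×√32 = 2.94. Power is 81.3% two-sided and 89.1% one-sided; the detectable effects at 80% are 0.51 and 0.45. The stated 0.52 fits the two-sided calculation, so the two power sentences appear to use different conventions. This is background only, since the within-arm sentence names no side.

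**The case against.** The best defence is that a one-sided test was meant all along. The power sentence says so openly, Aim 2 asks about superiority, and with a 1-df interaction a one-sided 0.05 test is the same contrast read by its sign (F at 0.10 in the favourable direction). That is the only level the plan gives for the between-arm comparison. On this reading power is 79.0% and the stated figure stands.

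Much of this is right. It rules out a charge of miscalculation, and it makes the 68% conditional on running the F test at 0.05, a level that the analysis text does not state. It does not remove the inconsistency. The analysis text specifies a significant interaction and asks whether the effect differs. It mentions neither a one-sided contrast nor an F test at 0.10 with a check of sign.

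It is also fair that 64 is a floor. Section 7.0 anticipates under 10% missing data, and section 5.5 reports complete primary-endpoint data in earlier studies. With 67 evaluable (33 and 34), power is 70.5% for the F test and 80.7% one-sided; with all 74, it is 74.9% and 84.1%. The shortfall shrinks but does not close.

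A reader might infer that Aim 2's p-value decides whether coaching enters a Phase III trial, or that a null result will be taken to show that coaching adds nothing. The documents do not say this. Section 1.2 describes learning whether coaching has potential to add to the effect as a goal, no decision rule is tied to the interaction p-value, and section 7.0 also plans between-group effect sizes (Hedges' g). Using different sidedness for the two aims is not in itself an error either.

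**Conclusion.** The point holds as an inconsistency between the power statement and the analysis. The 80% is right for a one-sided 0.05 test. The interaction test, as written and if run at 0.05, has about 68% power at d=0.62 with 32 per arm and about 75% with all 74 evaluable; with 32 per arm it reaches 80% only at d of about 0.71.

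These figures assume a two-level time factor, as the 8-week endpoint implies, equal arms, and d scaled to the SD of change. The 68% also assumes the 0.05 level, which the plan does not state for this test. The stronger reading, that the power was miscalculated or that the plan definitely runs a 68% test, is not supported.

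**What to change.** Before the data are seen, amend section 7.0 by one of two routes.

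- **(a) Keep the interaction F test.** State that it is run at two-sided 0.05, and restate the power: with N=64, about 68% at d=0.62 and 80% at d=0.71.
- **(b) Keep the one-sided figure.** Replace the interaction F test for Aim 2 with a one-sided 0.05 contrast on 8-week change (coaching better), equivalent to F at 0.10 in the favourable direction, and give the reason for one-sided testing.

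Either takes one or two sentences and no extra participants. The cost of (a) is a less favourable stated power; the cost of (b) is an explicit one-sided test that has to be justified. A sentence saying that later decisions about coaching will rest on the estimated difference and its confidence interval would be a useful option, but it is not needed to correct this point.
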